9.3.1.2 Methods

The following tabulations will be prepared:

- Demographic and other baseline characteristics (safety analysis set)

- Disease characteristics (safety analysis set)

9.4 Safety Analyses

9.4.1 Extent of Exposure

9.4.1.1 Items

Items for summary of exposure

- Number of treated cycles (in summary statistics)
- Number of treated cycles: [≥ 1 , ≥ 2 , ≥ 3 , ... ≥ 13]
- Total amount of dose taken
- Number of doses taken
- Dose intensity
Dose intensity will be calculated using the following formula:
 - $\text{Dose Intensity (mg/cycle)} = \text{Total amount of dose taken (mg)} / \text{Number of treated cycles}$
- Relative dose intensity
Relative dose intensity will be calculated using the following formula:
 - $\text{Relative Dose Intensity (\%)} = (\text{Total amount of dose taken [mg]} / \text{Total amount of dose expected per initial dose [mg]}) * 100$
- Dosing compliance
Dosing compliance will be calculated using the following formula:
 - $\text{Dosing compliance (\%)} = (\text{Total amount of dose taken [mg]} / \text{Total amount of dose expected [mg]}) * 100$The dose expected is defined as the scheduled dose level for a dosing day when the action on drug is not "held" or "discontinued".

Items for change in exposure

- Subjects with any dose reduced prescribed: [#Reasons]
- Subjects with any dose reduced non-prescribed: [#Reasons]
- Subjects with any dose held: [#Reasons]
- Subjects with any dose missed: [#Reasons]
- Subjects with any dose delayed: [#Reasons]
- Subjects with any dose discontinued permanently: [#Reasons]

9.4.1.2 Methods

The following tabulations will be prepared:

- Summary of exposure to MLN9708 (Safety analysis set)
- Summary of exposure to Lenalidomide (Safety analysis set)
- Summary of exposure to Dexamethasone (Safety analysis set)

- Change in exposure to MLN9708 (Safety analysis set)
- Change in exposure to Lenalidomide (Safety analysis set)
- Change in exposure to Dexamethasone (Safety analysis set)

9.4.2 Adverse Events

9.4.2.1 Items

- Treatment-emergent adverse events (TEAEs)
- Treatment-related adverse events
- Serious treatment-emergent adverse events
- Serious treatment-related adverse events
- Treatment-emergent adverse events leading to permanent discontinuation of study treatment
- Treatment-related adverse events leading to permanent discontinuation of study treatment
- Dose limiting toxicities (DLTs)

9.4.2.2 Methods

TEAEs are defined as adverse events or events resulting from exacerbation of complications that have occurred after the first dose of MLN9708.

Treatment-related adverse events are defined as TEAEs that relationship to study treatment is assessed as “Yes”.

The Medical Dictionary for Regulatory Activities (MedDRA) version 16.0 will be used to code all adverse events to a system organ class (SOC) and a preferred term (PT).

The following tabulations will be prepared:

- Summary of treatment-emergent adverse events (Safety analysis set)
- Summary of treatment-related adverse events (Safety analysis set)
- Subject incidence of treatment-emergent adverse events by system organ class and preferred term by grade (Safety analysis set)
- Subject incidence of treatment-related adverse events by system organ class and preferred term by grade (Safety analysis set)
- Subject incidence of serious treatment-emergent adverse events by system organ class and preferred term by grade (Safety analysis set)
- Subject incidence of serious treatment-related adverse events by system organ class and preferred term by grade (Safety analysis set)
- Subject incidence of treatment-emergent adverse events leading to permanent discontinuation of study treatment by system organ class and preferred term by grade (Safety analysis set)

- Subject incidence of treatment-related adverse events leading to permanent discontinuation of study treatment by system organ class and preferred term by grade (Safety analysis set)
- Subject incidence of treatment-emergent adverse events by preferred term in descending order of frequency (Any vs. grade 3 or higher events) (Safety analysis set)
- Subject incidence of treatment-related adverse events by preferred term in descending order of frequency (Any vs. grade 3 or higher events) (Safety analysis set)
- Subject incidence of serious treatment-emergent adverse events by preferred term in descending order of frequency (Safety analysis set)
- Subject incidence of serious treatment-related adverse events by preferred term in descending order of frequency (Safety analysis set)
- Subject incidence of treatment-emergent adverse events leading to permanent discontinuation of study treatment by preferred term in descending order of frequency (Safety analysis set)
- Subject incidence of treatment-related adverse events leading to permanent discontinuation of study treatment by preferred term in descending order of frequency (Safety analysis set)
- Subject incidence of dose limiting toxicities by preferred term in descending order of frequency by safety evaluation committee in cycle 1 (DLT analysis set)

A subject counts once for each SOC and PT for its worst grade.

All “by SOC and PT” and “by PT” tabulations are prepared by descending order of frequency for total of treatment groups and by alphabetical order.

Serious adverse event that occurred prior to first dose of MLN9708 will be presented in the listing.

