**Table 1-3. Most Common (≥ 20%) Treatment-Emergent Adverse Events (Study C16003, N=56)**

	Treatment-Emergent Adverse Events
Most Common (≥ 20%) Any Grade	Fatigue (57%) Skin rash (all terms) (50%) Thrombocytopenia (41%) Diarrhea (36%) Nausea (34%) Vomiting and fever (30% each) Cough (25%) Anorexia (23%) Neutropenia (21%)
Drug-Related Grade ≥3 in ≥ 2 Patients	Thrombocytopenia (n = 19) Neutropenia (n = 8) Fatigue (n = 5) Rash (all terms) (n = 5)

Data cutoff 12 October 2011

Fifteen patients have experienced drug-related serious adverse events involving thrombocytopenia, anemia, neutropenia, febrile neutropenia, nausea, vomiting, abdominal pain, chest pain (noncardiac), orthostatic hypotension, hypotension, hypophosphatemia, hyperuricemia, fever, chills, rash, pneumonia, hypoxia, pulmonary hypertension, fall, headache, fatigue, or dehydration. Five patients discontinued therapy due to a treatment-emergent adverse event; 3 patients due to events considered at least possibly related to MLN9708 (thrombocytopenia, pulmonary hypertension, and pruritic rash) and remaining 2 patients due to events related to disease progression (spinal cord

compression and bone pain). There have been 2 on study deaths reported as not related to MLN9708.

In Study C16004 (0.24, 0.48, 0.80, 1.20, 1.68, 2.23, 2.97, and 3.95 mg/m^2, weekly), 32 patients were enrolled as of 12 October 2011 and received treatment for 1 to 11 cycles (median, 2 cycles). One patient achieved a VGPR and one patient achieved a PR.

In Study C16004, 2 of 3 patients experienced protocol-defined DLT (Grade 3 rash, Grade 3 nausea, vomiting, and diarrhea) at a dose of 3.95 mg/m^2. Additional patients were enrolled and treated at 2.97 mg/m^2. One of 6 patients treated at 2.97 mg/m^2 experienced a DLT (Grade 3 nausea, vomiting, and diarrhea). The MTD of MLN9708 administered weekly was determined to be 2.97 mg/m^2.

Overall, 97% of patients experienced a treatment-emergent adverse event. Peripheral neuropathy was limited to Grade 1 or 2 in 3 patients; with all patients reporting baseline Grade 1 peripheral neuropathy at study entry. The most common ( $\geq 20\%$ ) treatment-emergent adverse events are shown in [Table 1-4](#).

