#### **1.4.2 Clinical Studies in Patients With Newly Diagnosed Multiple Myeloma**

Two ongoing clinical trials of Studies C16005 and C16006 in patients with newly diagnosed multiple myeloma are currently ongoing.

In Study C16005 where MLN9708 is administered weekly (1.68, 2.23, 2.97, and 3.95 mg/m^2) in combination with lenalidomide and dexamethasone (Rd), 15 patients have been enrolled as of 12 October 2011 and completed 1 to 9 treatment cycles (median, 5 cycles). No DLTs were seen at doses up to 2.23 mg/m^2. Three of 3 patients treated at the 3.95 mg/m^2 dose cohort experienced Grade 3 nausea and vomiting despite adequate antiemetic therapy; one of which additionally experienced Grade 2 syncope and in another patient the dose of lenalidomide was compromised such that they received < 80% of the planned doses. Subsequent patients were treated at one dose level below (2.97 mg/m^2) where one of 6 patients experienced a DLT (Grade 3 rash). The MTD of weekly MLN9708 in combination with Rd was established at 2.97mg/m^2. However with this dose, 3 of 6 patients experienced Grade 2 and 3 rash and had to discontinue lenalidomide. Therefore, the recommended dose was determined to be 2.23 mg/m^2 plus Rd in the phase 2 portion of the combination trial and phase 3 Rd combination trial.

To date, all 15 response-evaluable patients have achieved ≥ PR to therapy including 4 CRs, 4 VGPRs, and 7 PRs; 14 out of 15 patients achieved ≥ PR after Cycle 1, and all 15 achieved ≥ PR after Cycle 2.

Overall, all 15 patients experienced a treatment-emergent adverse event. Peripheral neuropathy was limited to Grade 1 or 2 in 3 patients. The most common (≥ 20%) treatment-emergent adverse events are shown in [Table 1-5](#).

**Table 1-5. Most Common ( $\geq 20\%$ ) Treatment-Emergent Adverse Events  
(Study C16005, N=15)**

	Treatment-Emergent Adverse Events
Most Common ( $\geq 20\%$ ) Any Grade	Fatigue (60%) Vomiting (53%) Anemia (40%) Diarrhea and nausea (33% each) Insomnia, peripheral edema, and thrombocytopenia (27% each)
Drug-Related Grade $\geq 3$ in $\geq 2$ Patients	Rash and vomiting (n = 2 each)

Data cutoff 12 October 2011

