### **3. EXPERIMENTAL PLAN**

#### **3.1 Study Design**

This is a phase 1, multicenter, single-arm, open-label, dose-escalation study to evaluate the tolerability, safety, and pharmacokinetics of MLN9708 administered alone or in combination with Rd in patients with relapsed and/or refractory multiple myeloma. This study consists of the following 4 cohorts.

- Cohort 1: MLN9708 4.0 mg
- Cohort 2: MLN9708 4.0 mg + Rd
- Cohort 3: MLN9708 5.5 mg
- Cohort 4: MLN9708 5.5 mg + Rd

Three subjects will be enrolled sequentially from cohorts 1 (MLN9708 4.0 mg alone) to 4. If a DLT occurs in one subject during DLT-assessment period, 3 additional subjects will be enrolled in the applicable cohort to evaluate the tolerability in a total of 6 subjects. If DLT occurs in 2 of the 3 subjects, the given dosage is considered intolerable. If DLT occurs in 2 of the 6 subjects, the sponsor will determine the tolerability to the given dosage after discussing with the Efficacy and Safety Evaluation Committee (ESEC).

The sponsor will evaluate the tolerability of MLN9708 on the basis of the safety data including DLT incidences during the DLT-assessment period. The sponsor will decide whether the next cohort will be studied and the dose of the next cohort in consultation with the ESEC, if necessary. If the current cohort is considered tolerable, the next cohort will be in the order of cohorts 2 (MLN9708 4.0 mg + Rd), 3 (MLN9708 5.5 mg alone), and 4 (MLN9708 5.5 mg + Rd). Even if a dosage is considered tolerable and transition to the next cohort is considered feasible, the next cohort may not be studied based on the results of the overseas clinical studies and the current study.

The additional written informed consent for extended treatment will be obtained before the first dose of MLN9708 in Cycle 2 from the subjects who meet the criteria in [“6.4 Criteria for Beginning the Next Cycle of Treatment”](#) and have no safety concern.

Subjects who do not give the consent will undergo end of study (EOS) visit on 29 days after the last dose of MLN9708 in Cycle 1. The subjects giving the consent can continue

the study treatment up to 12 cycles unless they meet the criteria in “[8.1 Removal of Subjects](#)” including evidence of progressive disease (PD) and intolerable toxicity. Subjects may remain on treatment after the 12 cycles if the investigator considers it beneficial for the subjects.

All subjects should undergo EOS visit on 29 days after the last dose of MLN9708.

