## 6.5 Dose Modification

### 6.5.1 MLN9708 Monotherapy

#### 6.5.1.1 Criteria for Dose Modification

Dose modifications of MLN9708 are not permitted in Cycle 1.

If dose modification is required in Cycle 2 or subsequent cycles, MLN9708 dose will be reduced by one level according to [Table 6-2](#). If multiple toxicities are noted, the dose should be interrupted or reduced according to the most severe toxicity guidelines ([Table 6-3](#) and [Table 6-4](#)). Toxicity will be assessed according to the Common Terminology Criteria for Adverse Events (CTCAE) version 4.03.

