9. STATISTICAL METHODS OF ANALYSIS

9.1 General Principles

- Tables will be tabulated by the following groups unless otherwise specified;
 - monotherapy treatment group
 - combination treatment group
 - total of all subjects
- Listings and figures are provided by treatment group unless otherwise specified.
- Continuous variables will be summarized descriptively using summary statistics (n, mean, standard deviation, median, max, and min).
- Categorical variables will be summarized using frequencies and percentages.
- The analyses will not be performed for N=1.
- The National Cancer Institute-Common Terminology Criteria for Adverse Events (CTCAE) Version 4.03 will be used for grading the adverse events and clinical laboratory abnormalities.
- International uniform response criteria for multiple myeloma (Durie et al, 2006) will be used for evaluating the tumor response.

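### Apart from the Cycle 1 DLT table, the adverse-event tables give cumulative incidence over treatment of unequal length, so the monotherapy and combination columns can differ through exposure alone

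*SAP*

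**What the plan says.** SAP 9.4.2.2 lists 14 tables of treatment-emergent or treatment-related events on the safety analysis set: two summaries, six by system organ class, preferred term and grade, and six by preferred term. A typical one is "Subject incidence of treatment-emergent adverse events by system organ class and preferred term by grade (Safety analysis set". The counting rule is "A subject counts once for each SOC and PT for its worst grade", and an event qualifies if it is among those "that have occurred after the first dose of MLN9708". The SAP gives no end to that window. Protocol 9.2 collects non-serious events up to each subject's end of study, and Protocol 7.2.3 puts that visit on Day 29 after the last dose (+21 days). The window is therefore bounded for each subject, but its length is set by that subject's treatment.

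Treatment length is not capped. Protocol 3.1 plans up to 12 cycles and adds: "Subjects may remain on treatment after the 12 cycles if the investigator considers it beneficial for the subjects". The default columns in SAP 9.1 are monotherapy, "combination treatment group" and total.

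The one table with a fixed period is the DLT table, which is for Cycle 1. SAP 9.4.1 tabulates treated cycles, dose intensity and dose changes, but does not link them to adverse events. No adverse-event table is planned by cycle, per unit of exposure or by time to onset.

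**The concern.** Adverse events are a primary endpoint in their own right (Protocol 10.1.1, SAP 6.1), listed separately from DLTs, and the tables set the two regimens side by side. The chance of ever having an event rises with cycles received. A column with longer treatment therefore shows more events at the same risk per cycle, and a reader could take the excess for added toxicity of the combination.

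Unequal length is foreseeable for three reasons:

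- **Overseas experience.** Protocol 1.4.1 says that subjects on weekly monotherapy (Study C16004) "received treatment for 1 to 11 cycles (median, 2 cycles". Protocol 1.4.2 says that subjects on the weekly Rd combination (Study C16005) "completed 1 to 9 treatment cycles (median, 5 cycles".
- **Sequential cohorts.** Cohorts enrol one after another, and the SAP allows for ongoing subjects and a data cutoff, so potential follow-up differs by cohort at any cut. This need not favour the same column as the overseas medians.
- **Selection.** Entry to Cycle 2 needs recovery criteria, no safety concern and fresh consent, so later cycles cover a selected subset.

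Cycle 1 is the natural common period. For monotherapy, Protocol 6.5.1.1 states: "Dose modifications of MLN9708 are not permitted in Cycle 1". Protocol 6.5.2.1 applies the same rule to MLN9708 in the combination.

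**Working it through.** **The plan's own figure.** The documents give no expected event rate, exposure ratio or power for this trial. The only size figure is 12 to 24 subjects, which reproduces as 4 cohorts × 3 = 12 and 4 × 6 = 24.

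**Inputs.** Cycles k = 2 and 5 are the overseas medians in Protocol 1.4.1 and 1.4.2. The per-cycle risk p of first onset is an assumption, equal in both columns and run over a range.

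**Formula.** Cumulative incidence over k cycles = 1 − (1 − p)^k. For p = 0.10: 1 − 0.9² = 19.0% and 1 − 0.9⁵ = 41.0%.

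| p per cycle | 2 cycles | 5 cycles | ratio |
|---|---|---|---|
| 0.01 | 2.0% | 4.9% | 2.46 |
| 0.05 | 9.8% | 22.6% | 2.32 |
| 0.10 | 19.0% | 41.0% | 2.16 |
| 0.15 | 27.8% | 55.6% | 2.00 |
| 0.20 | 36.0% | 67.2% | 1.87 |
| 0.30 | 51.0% | 83.2% | 1.63 |
| 0.50 | 75.0% | 96.9% | 1.29 |

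Under this model the ratio reaches 2 only when p is at most about 0.15, that is, when the 2-cycle incidence is at most 28%.

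**Less idealised versions:**

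- *Follow-up to the end-of-study visit.* The last dose is on Day 15 of the final cycle, plus 29 days. This gives (28 + 15 + 29)/28 = 2.57 cycles against (112 + 15 + 29)/28 = 5.57. The ratio is 2.01 at p = 0.05, 1.87 at 0.10 and 1.44 at 0.30.
- *Spread of durations.* Geometric with medians 2 and 5, cut off at the overseas maxima of 11 and 9 cycles. At p = 0.10 the incidence is 27.3% against 41.0%, ratio 1.50. The ratio is 1.57 at p = 0.05 and 1.28 at 0.30.
- *Early onset.* Risk after Cycle 1 is cut to a quarter, with p = 0.10 in Cycle 1: 1 − 0.9 × 0.975 = 12.3% against 1 − 0.9 × 0.975⁴ = 18.7%, ratio 1.52.
- *Risk proportional to a falling dose.* With an assumed 4.0, 4.0, 3.0, 3.0, 2.3 mg over five cycles and p = 0.10 at 4.0 mg: 1 − 0.9² × 0.925² × 0.9425 = 34.7% against 19.0%, ratio 1.83.
- *Other exposure gaps at p = 0.10.* 4 against 5 cycles gives 1.19, 3 against 5 gives 1.51, 6 against 12 gives 1.53, and 2 against 12 gives 3.78.

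**Check against the overseas tables** (Protocol Tables 1-4 and 1-5 and adjoining text), monotherapy against combination: fatigue 50% and 60% (1.20), vomiting 28% and 53% (1.89), diarrhea 31% and 33% (1.06), nausea 38% and 33% (0.87), thrombocytopenia 34% and 27% (0.79), any event 97% and 100% (1.03).

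**Check of two possible remedies at p = 0.30:**

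- Dividing subjects with a first event by total treated cycles gives 0.510/2 = 0.255 against 0.832/5 = 0.166, a ratio of 0.65. This is biased the other way, because cycles after the first event stay in the denominator.
- Counting cycles only up to the first event gives expected cycles of 1 + 0.7 = 1.70 and 1 + 0.7 + 0.49 + 0.343 + 0.2401 = 2.7731. Then 0.510/1.70 = 0.832/2.7731 = 0.30, a ratio of 1.0.

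A Cycle 1 table also has an expected ratio of 1.0 under equal risk (10% in each column at p = 0.10).

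**The case against.** The strongest reply is that the plan never sets out to compare the regimens. The study is descriptive, with sequential non-randomised cohorts of 3 to 6 and no statistical basis for their size. Eligibility also differs between regimens: the creatinine clearance threshold is 30 or 60 mL/min, and the thrombosis exclusion applies only to Rd. Equal exposure would not by itself isolate the toxicity of adding Rd. This stands, and so the point concerns how the tables will be read rather than a failed comparison.

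The cohort decision rests centrally on DLTs up to Cycle 2 Day 1, and the DLT table is limited to Cycle 1. This also stands. A reader might infer that the tolerability decision is compromised, but the documents do not support that.

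Exposure is summarised in SAP 9.4.1, and SAP 10 lists exposure by visit and adverse events by subject. A reader can therefore see an imbalance, although the summary tables do not give events per cycle at risk.

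Chance is large too. With an assumed 6 subjects per column and true incidences of 19% and 41%, the monotherapy column shows at least as many cases 29% of the time. A larger sample would not remove the exposure effect, however, and it can be avoided with data already collected.

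A reader might also infer that falling dose widens the gap, or that later events are reported under a dose no longer taken. If risk follows dose, the gap narrows (2.16 to 1.83 at p = 0.10), and the default columns are labelled by regimen, not by dose.

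**Conclusion.** The point holds as a limitation of a descriptive primary safety endpoint. Apart from the DLT table, every adverse-event table gives crude cumulative incidence over a window that follows treatment length. That length is uncapped and may differ between the columns.

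If it differs as overseas, exposure alone could produce a ratio of about 1.5, and up to about two for less common events. The ratio falls as events become more common and is close to 1 for near-universal ones. These figures rest on the 2 and 5 cycle medians, taken at an early cutoff from relapsed or refractory and newly diagnosed populations, and on an assumed risk per cycle. They illustrate the effect and do not forecast this trial.

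A reader might infer a general two-fold distortion. The documents do not support that. It needs a roughly constant per-cycle risk of about 15% or less as well as the borrowed gap in cycles, and four of the five common events reported in both overseas studies had ratios between 0.79 and 1.20. Those studies also differ in population and regimen, so they neither confirm nor exclude the effect here.

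**What to change.** In SAP 9.4.2.2:

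1. Repeat for Cycle 1 only (first dose to before the Cycle 2 dose) the two preferred-term tables of treatment-emergent and of treatment-related events, any grade against grade 3 or higher. State which day closes the window for a subject who never starts Cycle 2.
2. State that any side-by-side reading of the regimens uses these Cycle 1 tables, and that the cumulative percentages are read alongside the exposure tables of SAP 9.4.1.
3. Optionally, for selected preferred terms, give first events per subject-cycle at risk, counting each subject's cycles only up to the first event. The number of treated cycles derived in SAP 9.4.1.1 is a total and should not be used as this denominator.

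The cost is SAP wording and two repeated tables from data already collected. Item 3 needs a separate derivation for each term, which is why it is limited to selected terms. The downside is a few more pages of output with small numbers per column. Cycle 1 tables also say nothing about late-onset events, so the cumulative tables should stay.

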9.4.3 Clinical laboratory

9.4.3.1 Items

- Hematology
- Chemistry (including corrected calcium)
- Urinalysis

9.4.3.2 Methods

For the purposes of summarization in the tables, listings and figures, all laboratory values will be converted to standardized units.

The textbook range (Pagana KD and Pagana TJ, 2011) will be used for the grading of differential.

The following tables will be prepared for all evaluable clinical laboratory abnormalities:

- Subject incidence of hematology abnormalities at post-baseline by grade (Safety analysis set)
- Subject incidence of chemistry abnormalities at post-baseline by grade (Safety analysis set)
- Subject incidence of urinalysis abnormalities at post-baseline by grade (Safety analysis set)
- Maximum grade shift from baseline for hematology (Safety analysis set)
- Maximum grade shift from baseline for chemistry (Safety analysis set)
- Maximum grade shift from baseline for urinalysis (Safety analysis set)

The following table will be prepared for all categorical values:

- Worst category shift from baseline for urinalysis (Safety Analysis Set)

The following tables and figures will be prepared for all continuous values:

- Summary of maximum/minimum post-baseline values for hematology (Safety analysis set)
- Summary of maximum/minimum post-baseline values for chemistry (Safety analysis set)
- Summary of maximum/minimum post-baseline values for urinalysis (Safety analysis set)
- Line plot of hematology by subject (Safety analysis set)
- Line plot of chemistry by subject (Safety analysis set)
- Line plot of urinalysis by subject (Safety analysis set)

9.4.4 12-Lead Electrocardiograms

